12 SOURCE DOCUMENTS AND ACCESS TO SOURCE DATA/DOCUMENTS

All study survey information will be captured electronically and stored on secure, encrypted Rutgers University servers.

- Patient consents will be captured and recorded directly into the REDCap system.
- All Patient surveys will be recorded directly into REDCap via the following REDCap forms:

Patient Participants
Triage Case Report
Pre-Visit Patient Survey
End-of-Visit Patient Survey
Patient Participation Questionnaire
Testing Case Report

Testing results will be captured in the REDCap Testing Case Report in the following ways:

	LAB
Original Source	Secure e-mail
Document	
Storage of Original	Electronically stored on
Source Document	Rutgers server
Responsibility for	Research Clinical
Entering into REDCap	Director or Co-
	Investigator
Verification of Correct	PI or Chief of Clinical
Entry into REDCap	Protocol

All paper based study source documents will be maintained in the Rutgers School of Dental Medicine Clinical Research Center which is located on the D Level of the Dental School Building. All documents will be secured in a locked file cabinet in the center. Access to the Clinical Research Center is limited to research center personnel via a card reader.

Study staff will maintain appropriate medical and research records for this study, in compliance with ICH E6, Section 4.9 and regulatory and institutional requirements for the protection of confidentiality of participants. Study staff will permit authorized representatives of NIDCR and regulatory agencies to examine (and when required by applicable law, to copy) research records for the purposes of quality assurance reviews, audits, and evaluation of the study safety, progress, and data validity.

9/1/2023

13 QUALITY CONTROL AND QUALITY ASSURANCE

Quality Management (QM) measures will occur throughout this study to ensure adherence to protocol and collection of high quality data. QM activities include those measures done as part of daily standard operating procedures by staff at each site and by the data management controls built into the PREDICT REDCap to ensure adherence to the protocol and collection of complete and accurate data. QM activities will include activities undertaken at defined intervals to check that QM activities are taking place and study-related documents are up-to-date.

Staff Training

Training of all staff will be conducted and recorded in training logs. Each staff member has been identified by role. Records of completed training will be maintained in each study member's study personnel file kept on the SDM PREDICT box drive, Personnel Qualifications folder.

Training Modules	Who Will be Trained
Human Subjects, HIPAA	All Study Personnel
General Clinical Research Training	PI, Chief of Clinical Protocol
(Human Subjects, HIPAA)	
General Overall	All Study Personnel
(Study Purpose, Goals and Protocol)	
REDCap System Training	Research Clinical Directors and Research Assistants

Daily Operating Procedures

Quality management measures have been built into Clinical Protocol Core and site procedures.

Subject Completion Review

As this is a feasibility study, reviews of surveys and case reports to ensure completeness will not be completed, rather the number/percentage of incomplete survey's and forms will be analyzed as an outcome measure. Consent forms will be reviewed for completeness as part of the end-of-visit survey for patient subjects.

Data Management Controls

REDCap is a rich system which enables privileging, required data element entry and required data validation to be embedded into daily operations.

- **Privileging:** Every study staff member will be assigned a role which carries specific read/write/edit/delete privileges. Staff member will be assigned a role providing minimal rights sufficient to perform his/her responsibilities.
- **Structured Data:** Whenever possible, data will be collected via structured data responses rather than free-text. Structured data requires a respondent to check a valid response.
- **Data Validation:** Data fields will be established limiting responses to those that are reasonable. For example, year of birth would have a range of 2002 (corresponding to age 18 the youngest eligible) to 1920 (corresponding to age 100 more than sufficient to cover the age range of individuals having impacted 3rd molars extracted.)
- **Required Fields:** Whenever appropriate, fields have been made required so as to ensure completed forms and guestionnaires.

Structured responses are required for the CRFs so only valid responses can be recorded. In addition, REDCap has been programmed with all responses being required at time of completion. Validation rules are employed where possible.

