3 OBJECTIVES AND OUTCOME MEASURES

3.0 Rutgers Feasibility Study Outcomes

PILOT Objectives	Brief Description/Justification of Outcome Measure	Outcome Measured By	Time Frame
To Determine Patient Willingness to Participate	Willingness to participate is important in determining whether patients would be willing to participate in a large-scale study	Ratio of patients agreeing to participate as compared to all patients asked to participate Thoroughness of consent process and ability to ask questions	Willingness to Participate: Patients – at time of consent by patients Patients – at End-of-Study
To Determine Patient Willingness/Ability to Follow Thru with Triage, Testing and Survey Administration Procedures	Determining willingness and ability to follow thru with triage, testing and survey administration procedures is important for refining the survey procedures	% who complete the study % who complete surveys o Pre-Visit Patient Survey o End-of-Visit Patient Survey % who feel testing (Saliva procedure was easy to comply with o Specimen collection o Specimen preparation for shipping o Specimen storage o Timeliness of results o Reporting of results	% Complete Study: Patients – End-Of-Visit (Day 1) % All Surveys Completed: Patients – End-Of-Visit (Day 1) % Feel Testing Protocol was Easy to Comply With: Patients – End-Of-Visit (Day 1)
To Determine Ease of Use with REDCap Survey Instruments Patient Subject Start-of-Visit Survey End-of-Visit Survey Triage Survey	Determining the ease of use and completeness of the REDCap instruments enables refinement of the system	% who feel surveys are easy to complete due to administration method:	% indicating surveys were easy to complete due to administration method: • Patients – at end of patient visit % indicating survey questions were easy to understand: • Patients – End-Of-Visit (Day 1) % Surveys Completed: • Patients – End-Of-Visit (Day 1)

3.1 Primary Outcomes for Full Study (Data Collection is Being Performed to Determine Instrument Feasibility)

Full Study Objective	Brief Description/Justification of Outcome Measure	Outcome Measured By	Time Frame

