4 STUDY DESIGN

Description: This study will assess the feasibility of implementing one COVID-related testing procedure in the dental setting. Results from this study may provide preliminary data to inform a larger network-wide study grant application.

Study Population: The study population for this study will be patients seen at the Rutgers School of Dental Medicine.

Important Outcomes: For this study, important outcomes include percent of patients willing to participate and percent completing the protocol.

Single or Multicenter: Single- this study will utilize the Rutgers School of Dental Medicine's Newark facility.

Number of Study Groups/Arms: One (1)

Expected Duration of Subject Participation: Subjects will be actively participating in the study for 2 weeks.

Sequence of Procedures and Duration of Study Period: Consent Process

About two weeks prior to their scheduled dental visit, patients will be contacted by the dental office to determine their willingness to participate in the study. Patients who indicate interest will be sent an email link, which opens the consent. The consent will clearly outline participant expectations and offer the opportunity for potential participants to contact the office for more information as needed. Participants who fully understand the study and elect to participate will affirm their willingness to participate by clicking the "I agree to take part in this study" button at the end of the consent form. Once in the office to provide their saliva sample, patients will also be asked to provide signed informed consent.

Study Procedures

Study participants will be asked to do the following:

- Two weeks before the dental visit
 - o Complete an electronic survey: Patient Pre-Visit Survey
 - Questions explore perceptions of safety and comfort, reasons for delaying dental care, concerns about returning to dental care, safety precautions valued, importance of triage and testing, and demographics
 - Launched automatically after the completed consent
 - Receive a saliva collection kit by mail
- One week before the dental visit
 - o Complete a COVID-19 saliva test
 - Spit into a tube
 - Package as directed
 - Drop off the completed test kit at the dentist's office
- Day prior to the dental visit
 - Undergo a COVID-19 triage screening over the phone*
 - Screening includes symptom questions (presence or absence of):
 - fever or chills
 - cough
 - shortness of breath or difficulty breathing
 - fatigue
 - muscle and body aches

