5 STUDY POPULATION

5.1 Participant Inclusion Criteria

A **Patient** must meet all of the following criteria to be eligible to participate in the study:

- Be a patient being treated at the Rutgers School of Dental Medicine
- Be 18 years or older
- Be able to understand the informed consent.
- Provide signed and dated informed consent form
- Be able to understand all instructions for data collection instruments in English
- Be willing and able to comply with all study procedures, including having a COVID-19 test performed

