5.3 Strategies for Recruitment and Retention

Target Sample Size: 20 patients.

Target Sample Size by Gender, Race, Ethnicity, and Age: Study population will be drawn from patients at the Rutgers School of Dental Medicine. It is estimated that about ½ will be female, ½ male. All will be English speaking. Age range will be between 18 and 100 years of age. Racial and ethnicity background will be reflective of the respective populations at the Rutgers Schools of Dental Medicine with about 52% being African American and 33% Hispanic.

Study Population: The patient study population will be drawn from outpatient dental clinics located at Rutgers University School of Dental Medicine.

Inclusion of Women and Minorities and Individuals of All Ages:

Women: Women will be included in this study. Pregnant women are eligible to participate.

Minorities: Minorities will be included in this study.

Recruitment Strategies: Patients treated in the Rutgers School of Dental Medicine's Oral Medicine clinic will be recruited. If 20 patients cannot be recruited in the Oral Medicine clinic, recruitment will expand to the school's other clinics. It is not anticipated that there will be difficulties recruiting sufficient patients.

Retention: In order to minimize loss of study participants and/or incomplete data collection, the following activities will take place:

- The Research Clinical Director will work with the co-investigators responsible for recruiting subjects and completing surveys.
- Participants will receive compensation.

Compensation and Scheduled Payments: Patients who complete the protocol, including the post-visit survey will be provided \$100.

Additional Plans to Minimize Loss of Follow-up and Missing Data: The following will minimize loss of follow-up and/or missing data:

• When appropriate, REDCap survey data fields are set to "required".

REDCAP validation rules on data fields to limit responses to valid responses

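### Does the example birth-year limit of 2002 in Section 13 wrongly shut eligible young adults out of a REDCap field?

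*Combined protocol and SAP*

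**What the plan says.** The data-validation bullet in Section 13 says fields will accept only reasonable values. Its example is "year of birth would have a range of 2002 (corresponding to age 18 the youngest eligible) to 1920", with 1920 equated to age 100. The same sentence justifies the upper age by reference to people having impacted third molars removed.

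The age rules are elsewhere. Section 5.1 requires patients to "Be 18 years or older" and sets no upper limit. Section 5.3 adds "Age range will be between 18 and 100 years of age".

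On how such limits work, Section 5.3 lists "REDCAP validation rules on data fields to limit responses to valid responses" among the measures against missing data. Section 13 states that "REDCap has been programmed with all responses being required at time of completion". However, the bullet just before that statement, and Section 5.3, make fields mandatory only where that is suitable.

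On what could be affected, Section 3.0 counts the percentage "who complete surveys". Under Subject Completion Review, Section 13 says completeness reviews will not be carried out and that the number or percentage of incomplete surveys and "forms will be analyzed as an outcome measure". The Pre-Visit Survey, which includes demographics, is "Launched automatically after the completed consent" (Section 4).

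**The concern.** The limit is a calendar year, while eligibility is an age. The two agree in one year and drift apart by a year for each year that passes. The text available gives no enrolment year, but the pages carry an unlabelled 9/1/2023 date, which makes use after 2020 plausible.

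If the live field followed the example, an eligible patient of 18, 19 or 20 could find the true birth year refused. If the field were also mandatory, the patient could leave the form unfinished or enter a false year to get past it. The study measures form completion and has chosen not to chase incomplete forms, so a fault in the software could be counted as poor compliance by a patient. With a target of 20 patients, a single form is visible in the percentage.

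**Working it through.** **Inputs.** Limits 2002 and 1920 with their stated ages 18 and 100 (Section 13); minimum age 18 (Section 5.1); target of 20 patients (Section 5.3). The enrolment year is not given, so 2020 to 2023 is tried.

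**Reproducing the plan's figures.** 2020 − 2002 = 18 and 2020 − 1920 = 100. Both pairs are right for 2020 and for no other year, so there is no arithmetic error in the sentence.

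**Moving the enrolment year.** An adult is refused if born after 2002 but already 18. By subtraction, the latest birth year that gives age 18 is the enrolment year minus 18.

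| Enrolment year | Year − 2002 | Eligible birth years refused | Ages refused |
|---|---|---|---|
| 2020 | 18 | none | none |
| 2021 | 19 | 2003 | 18 |
| 2022 | 20 | 2003–2004 | 18–19 |
| 2023 | 21 | 2003–2005 | 18–20 |

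In each row only those in the youngest birth year who have had their 18th birthday count. The lower limit drifts harmlessly: 1920 corresponds to 101 in 2021 and 103 in 2023.

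**How many patients.** The documents give no age distribution. Assume that each birth year holds a share s of 0.005 to 0.02 of clinic adults and that half of the youngest year has turned 18. The refused birth-year equivalents are then b = 0.5, 1.5 and 2.5. With p = b × s and 20 patients:

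- expected number = 20p
- P(none) = (1 − p)^20
- P(at most one) = (1 − p)^20 + 20p(1 − p)^19

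| Year | p | Expected | P(none) | P(at most one) |
|---|---|---|---|---|
| 2021 | 0.0025–0.01 | 0.05–0.2 | 0.951–0.818 | 0.999–0.983 |
| 2022 | 0.0075–0.03 | 0.15–0.6 | 0.860–0.544 | 0.990–0.880 |
| 2023 | 0.0125–0.05 | 0.25–1.0 | 0.778–0.358 | 0.974–0.736 |

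One affected form at full enrolment is 1/20 = 5 percentage points.

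**What the limit touches.**

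- *Eligibility.* Section 5.1 decides this by age. The example was never an exact age check, even in 2020: on 1 September 2020, people born from 2 September to 31 December 2002 were still 17 and would have passed it. It works as a plausibility screen.
- *Consent and willingness to participate.* Willingness is recorded at consent, and the survey holding demographics opens only afterwards. Neither is affected.
- *Analysis.* Section 11.2 states that no sample size is calculated, and Section 11.3 plans frequencies only. Nothing there uses 2002 or 1920.
- *Completion percentages.* This is the only route to a result. It requires enrolment after 2020, a field built to the example, a mandatory field, a patient aged 18 to 20, and a form that stays unfinished.

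**The case for a change.** The strongest case for acting is that later enrolment is likely. The reference list includes an item published online on 27 May 2020, IRB approval must precede enrolment, and the Protocol Summary allows six months to enrol. Enrolment would fit wholly inside 2020 only if it opened by about 1 July of that year. This is also the only numeric validation limit the protocol states, and it claims to encode the youngest eligible age. The Pre-Visit Survey opens automatically after electronic consent, so staff may not be beside the patient when it is filled in. The repair would be a few words.

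The drift is real, and use after 2020 is plausible. The step from there to a damaged result is weak. The sentence is worded as an illustration of what a field would look like. Its third-molar reference points to another study, so it is poor evidence of how the live field was built. Whether year of birth is mandatory is unclear, because Section 13 says both that every response is required and that fields are required where appropriate.

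The plan also has ways to expose the fault. Section 4 has staff assist with surveys. The dashboard in Section 7.2.1 marks instruments started but not finished in red, and the PI or Chief of Clinical Protocol reviews each one. Section 7.2.3 puts the full birth date on the specimen label, so a false year could be checked. A field that refuses a true birth year would be put right as a software setting when first met, and that needs no amendment.

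**Conclusion.** No change to the plan is called for. The example is out of step with any enrolment year after 2020, but it is a clerical leftover in an illustrative sentence. The rule that governs entry is the age criterion in Section 5.1, which is clear and agrees with the 18-to-100 range in Section 5.3.

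The likely effect is zero or one patient of 20. Even in the worst case tried (2023, 2% per birth year) the expected number is 1.0, and the chance of at most one is 74%. The consequence would be up to 5 points per affected form on a descriptive completion percentage, and only if the form stayed incomplete despite staff help and the dashboard. These figures rest on the assumed share per birth year, half of the youngest year having turned 18, and a mandatory live field that copies the example; the documents establish none of these. Consent, willingness to participate and every planned calculation are the same either way.

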14 ETHICS/PROTECTION OF HUMAN SUBJECTS

14.1 Ethical Standard

The investigator will ensure that this study is conducted in full conformity with the principles set forth in The Belmont Report: Ethical Principles and Guidelines for the Protection of Human Subjects of Research, as drafted by the US National Commission for the Protection of Human Subjects of Biomedical and Behavioral Research (April 18, 1979) and codified in 45 CFR Part 46 and/or the ICH E6.

14.2 Institutional Review Board

The protocol, informed consent form(s), recruitment materials, and all participant materials will be submitted to the IRB for review and approval. Approval of both the protocol and the consent form(s) must be obtained before any participant is enrolled. Any amendment to the protocol will require review and approval by the IRB before the changes are implemented in the study.

14.3 Informed Consent Process

Informed consent is a process that is initiated prior to the individual agreeing to participate in the study and continues throughout study participation. Extensive discussion of risks and possible benefits of study participation will be provided to participants and their families, if applicable. A consent form describing in detail the study procedures and risks will be given to the participant. Consent forms will be IRB-approved, and the participant is required to read and review the document or have the document read to him or her. The investigator or designee will explain the research study to the participant and answer any questions that may arise.

For patient subjects, an electronic consent will be obtained before the Pre-Visit-Triage survey is completed. Prior to any other research activity, written consent will be obtained upon arrival at the clinic prior to any other study-related assessments or procedures.

Potential participants will be given the opportunity to think about it prior to agreeing to participate. They may withdraw consent at any time throughout the course of the study. A copy of the signed informed consent document will be given to participants for their records. The rights and welfare of the participants will be protected by emphasizing to them that the quality of their clinical care will not be adversely affected if they decline to participate in this study.

The consent process will be documented in the clinical or research record.

14.4 Exclusion of Women, Minorities, and Children (Special Populations)

Women and minorities will be eligible to participate. Children less than 18 years will not be able participate.

14.5 Subject Confidentiality

Subject confidentiality is strictly held in trust by the investigators, study staff, and the study sponsor(s) and their agents. This confidentiality is extended to cover testing of biological samples and genetic tests in addition to any study information relating to participants.

The study protocol, documentation, data, and all other information generated will be held in strict confidence. No information concerning the study or the data will be released to any unauthorized third party without prior written approval of the study sponsor.

The study monitor or other authorized representatives of NIDCR may inspect all study documents and records required to be maintained by the investigator, including but not limited to, medical records (office, clinic, or hospital) for the study participants. The clinical study site will permit access to such records.

Certificate of Confidentiality

To further protect the privacy of study participants, the Secretary, Health and Human Services (HHS), has issued a Certificate of Confidentiality (CoC) to all researchers engaged in biomedical, behavioral, clinical, or other human subjects research funded wholly or in part by the federal government. Recipients of NIH funding for human subjects research are required to protect identifiable research information from forced disclosure per the terms of the NIH Policy (https://humansubjects.nih.gov/coc/index - Certificates of Confidentiality (CoC) – Human Subjects). As set forth in 45 CFR Part 75.303(a) and NIHGPS Chapter 8.3, recipients conducting NIH-supported research covered by this Policy are required to establish and maintain effective internal controls (e.g., policies and procedures) that provide reasonable assurance that the award is managed in compliance with Federal statutes, regulations, and the terms and conditions of award. It is the NIH policy that investigators and others who have access to research records will not disclose identifying information except when the participant consents or in certain instances when federal, state, or local law or regulation requires disclosure. NIH expects investigators to inform research participants of the protections and the limits to protections provided by a Certificate issued by this Policy.

NIH Data Sharing Policies

As described in section 17, it is NIH policy that the results and accomplishments of the activities that it funds should be made available to the public (see https://grants.nih.gov/policy/shring.htm - NIH Sharing Policies and Related Guidance on NIH-Funded Research Resources). Pls and funding recipient institutions will ensure that all mechanisms used to share data include proper plans and safeguards to protect the rights and privacy of individuals who participate in NIH-sponsored research.

